4.4 Adverse Event Reporting

Adverse event (AE) reporting is summarized below with the specific requirements described under Section 4.4.4.

4.4.1 Definitions

Adverse Event: Any untoward medical occurrence in a patient or clinical investigation subject administered a pharmaceutical product and which does not necessarily have a causal relationship with this treatment. An adverse event (AE) therefore is any unfavorable and unintended sign (including an abnormal laboratory finding), symptom, or disease temporally associated with the use of a medicinal (investigational) product, whether related or not related to the IMP/PTM medicinal (investigational) product.

An adverse event can be Anticipated or Unanticipated

- **Anticipated adverse events** are those that have been previously identified as resulting from the underlying disease, the HCT, or acute GVHD and not related to study drug. Investigator should refer to the anticipated event list (see Appendix E) to assess whether or not an event is anticipated. Anticipated events will be collected in the data capture system through calendar-driven forms (Toxicity, GVHD, etc.) and event-driven forms (Death, Infection, etc.). Events that meet serious criteria should be reported as detailed in Section 4.4.4.2.
- **Unanticipated adverse events** are those that vary in nature, intensity, or frequency from information in the current anticipated event list, the Investigator's Brochure, the package insert, or when it is not included in the informed consent document as a potential risk. Unanticipated events would also include those that have not been previously described as a result of the underlying disease requiring HCT, the HCT or acute GVHD.

The following are anticipated adverse events and do NOT require reporting as an AE/SAE:

- Disease progression of primary malignancy
- GVHD and symptoms of GVHD (these are recorded in acute and chronic GVHD eCRFs)
- Infections
- Graft failure
- Medical or surgical procedures (the condition that leads to the procedure is the AE)
- Situations where an untoward medical occurrence has not taken place. For example:
 - Planned hospitalizations due to pre-existing conditions, which have not worsened (e.g., HCT)
 - Hospitalizations that occur for procedures not due to an AE (e.g., cosmetic surgery)
 - Hospitalizations for a diagnostic procedure where the hospital stay is less than 24 hours in duration or for normal management procedures (e.g., chemotherapy)
 - Overdose of AAT or any concomitant therapy that does not result in any adverse signs or symptoms. (An overdose is a dose higher than the dose established in the protocol. For this study, the protocol dose is 120 mg/kg. There is a 5% variance that is allowed due to the rounding permitted in the preparation of the IMP. Therefore, an

AAT dose \geq 1.06% of 120 mg/kg (i.e., 126 mg/kg) that does not result in any adverse signs or symptoms would not require reporting as an AE/SAE.)

Laboratory findings do NOT need to be reported as AEs in the following cases:

- Laboratory parameters already beyond the reference range at screening, unless a further increase / decrease can be considered an exacerbation of a pre-existing condition.
- Abnormal hematological laboratory parameters considered anticipated due to myeloablative conditioning regimen or other permitted chemotherapy treatments are not considered AEs.
- An abnormal laboratory value that cannot be confirmed after repeat analysis, preferably in the same laboratory (i.e., the previous result could be marked as not valid and should not necessarily be reported as an AE).

Serious Adverse Event: A serious adverse event (SAE), as defined by per 21 CFR 312.32, is any adverse event that results in one of the following outcomes, regardless of causality, anticipation, and/or expectedness:

- **Results in death**
- **Is life-threatening.** Life-threatening means that the person was at immediate risk of death from the reaction as it occurred, i.e., it does not include a reaction which hypothetically might have caused death had it occurred in a more severe form.
- **Requires or prolongs inpatient hospitalization** (i.e., the event required at least a 24-hour hospitalization or prolonged a hospitalization beyond the expected length of stay). Hospitalization admissions and/or surgical operations scheduled to occur during the study period but planned prior to study entry are not considered SAEs if the illness or disease existed before the person was enrolled in the trial, provided that it did not deteriorate in an unexpected manner during the trial (e.g., surgery performed earlier than planned).
- **Results in persistent or significant disability/incapacity.** Disability is defined as a substantial disruption of a person's ability to conduct normal life functions.
- **Is a congenital anomaly or birth defect; or**
- **Is an important medical event** when, based upon appropriate medical judgment, it may jeopardize the participant and require medical or surgical intervention to prevent one of the outcomes listed above. Examples of such medical events include allergic bronchospasm requiring intensive treatment in an emergency room or at home; blood dyscrasias or convulsions that do not result in inpatient hospitalization, or the development of drug dependency or drug abuse.

Medical and scientific judgment should be exercised in deciding whether reporting is also appropriate in situations other than those listed above. For example, important medical events may not be immediately life threatening or result in death or hospitalization but may jeopardize the subject or may require intervention to prevent one of the outcomes listed in the definition above (e.g., suspected transmission of an infectious agent by a medicinal product is considered a

Serious Adverse Event). Any event is considered a Serious Adverse Event if it is associated with clinical signs or symptoms judged by the Investigator to have a significant clinical impact.

4.4.2 Classification of Adverse Events by Severity

The severity refers to the intensity of the reported event. The Investigator must categorize the severity of each SAE according to the National Cancer Institute (NCI) CTCAE Version 5.0. CTCAE guidelines can be referenced at the following website: https://ctep.cancer.gov/protocoldevelopment/electronic_applications/docs/CTCAE_v5_Quick_Reference_5x7.pdf. For any term that is not specifically listed in the CTCAE scale, intensity will be assigned a grade of one through five using the following CTCAE guidelines:

- Grade 1: Mild; asymptomatic or mild symptoms, clinical or diagnostic observations only; intervention not indicated
- Grade 2: Moderate; minimal, local or noninvasive intervention indicated; limiting age-appropriate instrumental activities of daily living
- Grade 3: Severe or medically significant but not immediately life-threatening; hospitalization or prolongation of hospitalization indicated; disabling; limiting self-care activities of daily living
- Grade 4: Life-threatening consequences; urgent intervention indicated
- Grade 5: Death related to AE

4.4.3 Classification of Adverse Events by Relationship to Investigational Product

The relationship of each reported event to the study therapy will be assessed by the Investigator; after careful consideration of all relevant factors such as (but not limited to) the underlying study indication, coexisting disease, concomitant medication, relevant history, pattern of the SAE, temporal relationship to any study therapy interventions and dechallenge or rechallenge according to the following guidelines:

- **Possibly, Probably, or Definitely Related:** there is a reasonable possibility that the study therapy caused the event. A relationship of possibly, probably, or definitely related to the investigational product is considered **related** for the purposes of regulatory authority reporting.
- **Unlikely, or Not Related:** There is no reasonable possibility that the investigational product caused the event. An unlikely or not related relationship to the investigational product is considered **not related** for the purposes of regulatory authority reporting.

4.4.4 Required Adverse Event Reporting

4.4.4.1 Non-Serious Adverse Events

All non-serious adverse events will be reported from randomization until 30 days after the last dose of study drug (AAT/PTM). Some anticipated non-serious events will be collected on calendar-driven forms or event-driven forms (Infection, GVHD, Graft Failure, Readmission/Hospitalization, and Progression/Relapse).

4.4.4.2 Serious Adverse Events (SAE)

All SAEs will be reported from randomization until 30 days after the last dose of study drug (AAT/PTM). In addition, any SAE assessed as related to the investigational product that occurs after the 30-day follow-up period must be reported. Any unanticipated SAE from 31 days after the last dose of study drug through the study defined follow up (1-year post enrollment) are required to be reported through the expedited AE reporting system in Advantage eClinical. **Additionally, any grade 4 anticipated event not collected on the calendar-driven toxicity or specified event-driven form must also be reported through the expedited AE reporting system in Advantage eClinical. For this study, the reporting will be based on unanticipated in place of the MOP definition of unexpected.**

All reported SAEs are to be followed up until resolved, the Investigator judges an event as no longer clinically significant, or until the event stabilizes/becomes chronic to the extent that the event can be fully characterized.

Serious adverse events (SAEs) will be reported through an expedited AE reporting system via electronic data capture. Life-threatening and fatal SAEs must be reported within 24 hours of knowledge of the event. All other SAEs must be reported within 1 business day of knowledge of the event. Events entered in the EDC will be reported using NCI's CTCAE Version 5.0.

The Data and Safety Monitoring Board will receive reports of all unanticipated/unexpected SAEs upon review by the BMT CTN Medical Monitor and CSLB. Summary reports for all reported SAEs will be reviewed by the DSMB on at least an annual basis.

4.4.4.3 Adverse Events of Special Interest (AESI)

The Sponsor has a list of events classified as Adverse Events of Special Interest (AESI). These include 'anaphylactic infusional reaction' and 'suspected transmission of a viral agent via a medicinal product.' Both events must be reported through the expedited AE reporting system via Advantage eClinical and must be reported within 24 hours of knowledge of the event even if it does not meet serious criteria.

4.4.4.4 Toxicity Reporting

Toxicities are a subset of anticipated adverse events determined to be from the underlying disease process, HCT, GVHD prophylaxis, or corticosteroid use, and generally are not considered to be related to the study product. The toxicities listed in APPENDIX E were pre-determined by the Protocol Team.

Once the participant has reached 31 days from last dose of study drug, toxicities listed in APPENDIX E should be reported at the specified time points on the Toxicity CRF. **If an event listed is determined to be serious and related to AAT, it should be reported via the expedited reporting process on the AE/SAE case report form (CRF).**

4.4.5 Pregnancy

A female subject or female partner of a male subject who becomes pregnant from randomization up to and including 30 days after the last dose of study drug, must notify the Investigator immediately. CSLB must be notified within 5 days of the Investigator becoming aware of the pregnancy.

If a female subject becomes pregnant, she must discontinue treatment with the study drug but may continue other study procedures at the discretion of the Investigator.

Whenever possible, a pregnancy in a subject or in a female partner of a male subject exposed to study drug should be followed to term to assess any potential occurrence of congenital anomalies or birth defects. Any follow-up information, including premature termination and the status of the mother and child after delivery, should be reported by the Investigator through the expedited AE reporting system in Advantage eClinical. All abnormal pregnancies and neonatal outcomes (e.g., spontaneous abortion, stillbirth, neonatal death, or congenital anomaly) will meet the criteria for SAE classification. The Investigator should follow the procedure for reporting these events as SAEs.

CHAPTER 5

5 STATISTICAL CONSIDERATIONS

5.1 Study Design

This study is a phase III, multicenter, double-blinded, randomized, placebo-controlled trial designed to compare AAT and corticosteroids (CS) to placebo-to-match (PTM) and CS as first-line therapy for patients with high-risk acute GVHD.

The study consists of an interim analysis for futility and a 12-month analysis at the end of the study. An additional analysis will be conducted after all randomized patients in the study complete 6 months of follow-up. Multiplicity adjustment is not needed for this analysis as all the patients would have completed the Day 28 primary endpoint visit by the time of analysis.

The target enrollment is 136 patients from approximately 25 centers with 68 patients assigned to each arm.

5.1.1 Accrual

It is estimated that an accrual period of 36 months (assuming a steady state of 4 patients per month after ramp up) will be necessary to enroll the target sample size. Accrual will be reported by race, ethnicity, gender, and age.

5.1.2 Randomization

Following enrollment, patients will be stratified by centers and randomized within each center in a 1:1 ratio using permuted blocks of random sizes for the two treatment arms.

Treatment practices differ considerably by centers. This includes the time to declare a patient refractory to steroids and potentially initiate next-line therapy. The variability by center may produce greater differences in treatment groups compared with age (adolescent vs adult), GVHD risk or disease. Additionally, the pathobiology of GVHD in both adolescent and adult and in malignant and non-malignant disease patient populations are similar. Therefore, since the presentation of GVHD and the anticipated response to treatment are expected to be similar, center was prioritized as the primary stratification variable.

5.1.3 Primary Endpoint

The primary endpoint is the proportion of participants with an overall (complete or partial) response to acute GVHD treatment at Day 28 post-randomization. Patients without a Day 28 response assessment will be considered failures. Acute GVHD will be graded and assessed for response based on Harris Criteria (refer to APPENDIX C). Patients who receive next-line systemic GVHD therapy (or escalation of steroids to ≥ 2.5 mg/kg/day of prednisone [or methylprednisolone equivalent of 2 mg/kg/day]) before Day 28 will be classified as NR. Responses categorized as NR, MR and progression will be treated as a failure for the primary endpoint. The primary analysis will be performed using the intent-to-treat principle. Therefore, all randomized patients will be included in the primary analyses.

5.1.4 Primary Hypothesis

The primary null hypothesis is that the odds ratio for response (CR/PR) at Day 28 between the treatment groups, adjusted for center, is equal to 1 versus the alternative hypothesis that the odds ratio is greater than 1 (AAT+CS versus PTM+CS). Therefore, an odds ratio greater than one means the response rate is higher in the AAT+CS group compared with the PTM+CS group. This null hypothesis will be tested using a one-sided significance level of 2.5%.

5.2 Sample Size and Power Calculations

The primary analysis will be based on a Wald test from a mixed effects logistic regression to test the odds ratio for response between the groups, adjusted for center and GVHD risk (Group A vs Group B; see Section 2.4.1, #3) as described in Section 5.6. We approximate the sample size and power requirements for this study based on a two-sample Z test of response rates. Historical control data indicates that the overall response rate (CR/PR) at Day 28 for high risk acute GVHD is approximately 50%. We further anticipate that the treatment will increase response rate to 75%. We planned a single boundary (nonbinding futility) design for testing a one-sided hypothesis with one interim analysis for futility, when 56% of the information is evaluable (76 patients or 38 per arm), and a 12-month analysis using a design based on the Gamma family spending function with parameter $\gamma = -8$. Therefore, a sample size of 136 patients (68 per arm) is required to sufficiently maintain a one-sided type I error of 2.5% while providing 86% statistical power for a one-sided test to detect an effect size of 25%. All statistical analyses will be done using SAS Version 9.4 or higher or R Version 3.4.4 or higher.

5.3 Study Analysis Schedule and Safety Stopping Guidelines

The study will consist of an interim analysis for futility after 56% of the patients (n=76) are evaluable, at a time coincident with a regularly scheduled meeting of the NHLBI-appointed DSMB, and a 12-month analysis after accrual and follow up for the primary endpoint is complete.

An additional analysis will be conducted after all the randomized patients in the study complete 6 months of follow-up post-randomization. This analysis is conducted to expedite the primary endpoint evaluation for potential regulatory submission. Multiplicity adjustment is not needed for this analysis as all the patients would have completed the Day 28 primary endpoint visit by the time of analysis. The details for this 6-month analysis, including the data to be included, will be specified in the statistical analysis plan.

Policies and composition of the DSMB are described in the BMT CTN's Manual of Procedures. The stopping guidelines serve as a trigger for consultation with the DSMB for additional review and are not formal "stopping rules" that would mandate automatic closure of study enrollment. Toxicity, adverse events, and other safety endpoints will be monitored regularly and reported to the DSMB at each meeting.

5.3.1 Interim Analysis for Futility

Analyses will be performed as described below in Section 5.6 for the primary endpoint. At the interim analysis time point, a Wald test for testing whether the odds ratio is equal to 1 in a mixed effects logistic regression model will be compared to the critical values shown in Table 5-1. All patients with at least 28 days of follow-up post randomization prior to the time of the interim analyses will be used to compute this statistic. Therefore, if the response rate in the placebo group

[figure not shown]
is at least 0.034 or higher than the AAT group, the DSMB will make a recommendation regarding termination or continuation of the trial.

Non-binding futility stopping rules—maintaining type I error control even if not followed exactly—were obtained from the Gamma family spending function with shape parameters $\gamma = -8$. This boundary corresponds to a conditional power of 8.9% under the alternative. This would also correspond approximately to an effect size (on a difference in response rates scale) less than -0.034 (Figure 5-1) or a Z statistic less than -0.31. In other words, if we were to observe a test statistic of -0.31 or smaller at the interim analysis, there is only an 8.9% chance that the study would be statistically significant at the 12-month analysis, under the alternative hypothesis.

Table 5-1 Single Boundary Non-Binding Futility Stopping Thresholds with One-Sided Type I Error 2.5%, Power 86% and an Effect Size of 25%

Info. Fraction	Sample Size	Nominal Cumulative Type II Error Rate	Futility Boundary Scales				Probability of Stopping Early for Futility
			Difference in Proportions	Z-Statistic	Conditional Power Under Alternative	Under Null	
0.56	76	0.004	-0.034	-0.31	0.089	0.378	0.004
1.0	136	0.139	0.163	1.96			

Figure 5-1 Stopping Boundary on Difference in Proportions Scale

5.3.2 Operating Characteristics of the Design

The statistical power to reject the null hypothesis under various treatment effect sizes using the Z test for comparing binomial proportions is shown in Table 5-2 as an approximation to the power using the primary analysis of mixed effects logistic regression. Kahan and Morris (2012) showed that a stratified analysis improves statistical power. Therefore, the unadjusted power analysis is a conservative estimate of the actual power. Also shown are the stopping probabilities for futility

at each effect size for the interim and 12-month analysis. This table shows that the target sample size of 136 patients has 86% power to detect a 25% difference in the response rate and is based on a simulation study with 10,000 simulated datasets.

Table 5-2 Summary of Operating Characteristics

Effect Size	Expected Sample Size	Overall Cumulative Power	Probability of Stopping Early
0.00	114	2.3%	0.360
0.10	129	21.24%	0.110
0.15	133	41.9%	0.046
0.20	135	65.2%	0.015
0.25	136	85.9%	0.003

5.3.2.1 Stratified Mixed Effects Logistic Simulation

We simulated a stratified randomized block design using blocks of size 6, based on the distribution of patients observed in each center of the BMT CTN 1501 study. Centers with fewer than 10 patients were combined resulting in a total of 6 centers of size 23, 19, 17, 15, 14 and 48. We assumed these centers are a random sample from a larger population with standard deviations 0.05, 0.6 and 1.0. Additionally, we estimated that 35% of the patients will be classified as “high risk”; a covariate that we adjust for in all the simulations done

Simulation results indicate that in the absence of a random effect (i.e., when the standard deviation of the random effect is close to zero) our statistical power is at least 94.2% to detect an odds ratio of 3. Further, when the random effect is present (std. dev. of 0.6 and 1.0) statistical power is at least 92.9% and 90.1% to detect an odds ratio of 3 as shown in Table 5-3. We also obtain statistical power ranging from 20.8% to 25.5% when the odds ratio is 1.5 regardless of the variability between centers.

Table 5-3 Stratified Mixed Effects Logistic Model with 1000 Simulations of Size 136

Effect Size	Power (%)				
	Variance of Random Effects				
AAT - PTM	Odds Ratio	Coef.	0.0025	0.36	1.0
10%	1.500	0.406	25.5	24.2	20.8
15%	1.857	0.619	53.8	51.3	48.4
20%	2.500	0.916	85.0	83.4	79.6
25%	3.000	1.099	94.2	92.9	90.1

5.3.3 6 Month Analysis for Clinical Study Report

A clinical study report for potential regulatory submission will be prepared after all randomized subjects have completed at least 6 months of follow-up post-randomization. The database will be locked to support this clinical study report. Data transfer and unblinding will follow the study's Blinding Management Plan. This report will include descriptive statistics based on available data at time of the analysis as well as formal hypothesis testing / treatment comparisons for the primary Day 28 overall response rate (CR/PR) endpoint and secondary endpoints including GVHD-free

survival, proportion of response, proportion of response allowing for next-line therapy, and systemic infections.

The BMT CTN 1705 Statistical Analysis Plan (SAP) will elaborate further on the contents of the 6-month report.

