4.3 SIMULATION STUDY

A simulation study was conducted to evaluate the power provided by a logistic mixed model in this sequential design. Randomized treatment assignments were generated for each simulated trial using stratified randomized block design at a 1:1 ratio with permuted blocks of size 6, with center accrual numbers obtained from those observed in participating centers of the BMT CTN 1501 study. Centers with fewer than 10 patients were combined, resulting in 6 center-groups of size 23, 19, 17, 15, 14, and 48. We assumed these groups' random effects are a random sample from a zero-mean normal distribution. Additionally, we estimated that 65% of the patients would be classified as Refined Minnesota high risk, with GVHD risk (MN high vs. standard) included as a fixed effect in the logistic model for all simulations. We considered possible effect sizes of 10%, 15%, 20%, and 25% and standard deviations for the random effects of 0.05, 0.60, and 1.00, with 1000 replicated trials simulated for each scenario.

Simulation results in Table 5 indicate that, in the near absence of a random effect (i.e., when the standard deviation of the random effect is close to zero), the statistical power is at least 94.2% to detect an odds ratio of 3.0, corresponding to an effect size of 25%. Further, when the random effect is present (standard deviation of 0.6 or 1.0), statistical power is at least 92% and 90% to detect an odds ratio of 3.0. For any other given effect size, the power levels are similar regardless of the variability of the random effects. These results support the ability of the logistic mixed model to provide at least 86% power in this group sequential design.

Table 5: Empirical Power for Logistic Mixed Model (1000 simulations per scenario)

Effect Size (AAT vs. PTM)		Power (%)		
		Standard Deviation of Random Effects		
Difference in Day 28 CR/PR		Odds Ratio	0.05	0.60
10%		1.500	25.5	24.2
15%		1.857	53.8	51.3
20%		2.500	85.0	83.4
25%		3.000	94.2	92.9
				90.1

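### The 20% row of the mixed-model power table uses odds ratio 2.5, but 50% to 70% is 2.333, which overstates power for a 20-point effect by about 5 to 7 points

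*Protocol*

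**What the plan says.** Protocol section 5.2 fixes the planning rates. For control, "Historical control data indicates that the overall response rate (CR/PR) at Day 28 for high risk acute GVHD is approximately 50" percent; for the new treatment, "We further anticipate that the treatment will increase response rate to 75" percent. The test is one-sided at 2.5% (section 5.1.4), with 68 patients per arm (section 5.1).

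Two power tables follow. Table 5-2 (section 5.3.2) uses the unadjusted Z-test; its 20-point row is "0.20 135 65.2% 0.015", that is, 65.2% power. Table 5-3 (section 5.3.2.1) gives simulated power for the mixed logistic model and pairs each difference in response rate with an odds ratio and a coefficient. Its first row is "10% 1.500 0.406 25.5 24.2 20.8". Its third row, the one at issue, is "20% 2.500 0.916 85.0 83.4 79.6".

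SAP section 4.3 describes the same simulation in terms of differences: "We considered possible effect sizes of 10%, 15%, 20%, and 25" percent. SAP Table 5 again pairs 20% with 2.500. It has no coefficient column.

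**The concern.** A difference in proportions fixes an odds ratio only once a control rate is chosen. Three rows of Table 5-3 use 50%, the rate planned for the trial. The 20% row fits neither that rate nor any other that the documents give for it.

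It is also the only mixed-model power printed between 15 and 25 points. It is therefore where a reader would look to see how the primary analysis fares if the benefit falls somewhat short of the target. If the row was simulated at a larger effect than its label says, the power shown for a 20-point benefit is too high in all three columns and in both documents.

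**Working it through.** **Inputs.** Control rate 50% (Protocol 5.2); 68 per arm (5.1); one-sided 2.5%, z = 1.96 (5.1.4); differences, odds ratios, coefficients and powers from Table 5-3.

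**Step 1: conversion.** With control rate 0.5 the control odds are 1, so OR = p1/(1 − p1).

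| Label | p1 | OR from 50% | ln OR | Printed OR | Printed coefficient |
|---|---|---|---|---|---|
| 10% | 0.60 | 1.500 | 0.405 | 1.500 | 0.406 |
| 15% | 0.65 | 1.857 | 0.619 | 1.857 | 0.619 |
| 20% | 0.70 | 2.333 | 0.847 | 2.500 | 0.916 |
| 25% | 0.75 | 3.000 | 1.099 | 3.000 | 1.099 |

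Only the 20% row fails. In reverse, OR 2.5 gives p1 = 2.5/3.5 = 0.714, a 21.4-point difference. An odds ratio of 2.5 equals 20 points only at control rates near 24% or 56%.

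**Step 2: typing slip, or the value simulated?** The printed 0.916 is ln 2.5, so odds ratio and coefficient agree with each other. The powers can be tested as well. Convert the other three rows to probits, pass a quadratic in ln OR through them, and read it off at the two candidates. For the lowest-variance column the probits of 25.5%, 53.8% and 94.2% are −0.659, 0.095 and 1.572.
- Divided differences: (0.095 + 0.659)/0.2136 = 3.53; (1.572 − 0.095)/0.4796 = 3.08; second difference (3.08 − 3.53)/0.6931 = −0.65.
- At ln 2.5: −0.659 + 3.53 × 0.511 − 0.65 × 0.511 × 0.297 = 1.045, or 85.2%.
- At ln 2.333: −0.659 + 3.53 × 0.442 − 0.65 × 0.442 × 0.228 = 0.835, or 79.8%.

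| Random-effect SD | Printed | Predicted at OR 2.5 | Predicted at OR 2.333 | Printed minus OR 2.333 |
|---|---|---|---|---|
| 0.05 | 85.0 | 85.2 | 79.8 | 5.2 |
| 0.6 | 83.4 | 83.1 | 77.4 | 6.0 |
| 1.0 | 79.6 | 80.2 | 74.6 | 5.0 |

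The printed powers sit on the OR 2.5 prediction in every column.

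**Step 3: size at the stated N and alpha.** Pooled Z-test: power = Φ[(d − 1.96·SE0)/SE1], with SE0 = √(2·p̄(1 − p̄)/68) and SE1 = √((p0(1 − p0) + p1(1 − p1))/68).
- Plan's own design case, 50% v 75%: (0.25 − 1.96 × 0.0830)/0.0802 = 1.088, or 86.2%. The 86% is reproduced.
- 50% v 70%: (0.20 − 1.96 × 0.0840)/0.0822 = 0.430, or 66.6%, close to the 65.2% in Table 5-2.
- 50% v 71.4%: (0.2143 − 1.96 × 0.0838)/0.0817 = 0.613, or 73.0%.

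The conversion is worth 73.0 − 66.6 = 6.4 points.

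**Step 4: mixed model.** A simulation with the stated center sizes, blocks of 6, a random intercept and a Wald test used 2,000 replicates per cell (Monte Carlo standard error about 1 point). The documents give no size for the risk effect, so two settings were assumed: none with 35% high risk, and log odds ratio −0.5 with 65% high risk.

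| SD | OR 2.333 | OR 2.5 | Gap |
|---|---|---|---|
| 0.05 | 66.9 / 66.1 | 73.0 / 72.6 | 6.1 / 6.5 |
| 0.6 | 63.2 / 62.2 | 69.4 / 69.0 | 6.2 / 6.8 |
| 1.0 | 58.0 / 56.7 | 64.5 / 63.8 | 6.5 / 7.1 |

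All three routes put the effect of the conversion at about 5 to 7 points.

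**The case against.** **Little depends on this row.** This stands. N=136 and the 86% power rest on the Z-test at 50% v 75%. The text of section 5.3.2.1 cites only odds ratios 3 and 1.5. The SAP's conclusion of at least 86% power draws on the 25% row; the 20% row prints below 86% throughout. No test, boundary or decision rule uses it. The odds ratio is also printed beside the label, so a careful reader can see the mismatch.

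**The model's odds ratio is conditional on center.** Averaged over centers around a 50% control rate, odds ratio 2.5 is 21.4, 20.0 and 18.2 points at SD 0.05, 0.6 and 1.0, so 20% is about right in the middle column. As arithmetic this stands, and it limits the 21.4-point figure to a center with a 50% control rate. It does not explain the row: the other three rows use the center-level conversion in all columns, and the near-zero-variance column is wrong on either reading.

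**The whole table runs high.** This also stands. The 25% row has the right odds ratio, yet prints 94.2% against about 86% by formula. The 15% row prints 53.8% against 41.9% in Table 5-2. That is a separate problem, and it does not remove the conversion error.

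**Conclusion.** The 20% row in both documents was labelled, and almost certainly simulated, at the wrong odds ratio. From the 50% control rate of the other rows it should be 2.333. The overstatement of power for a 20-point effect due to this alone is about 5 to 7 points. This rests on the 50% control rate and, for the table-footing figures, on a smooth power curve through the other three rows.

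A reader might infer three stronger things that the documents do not support:
- That 85.0% is the correct power for a 21.4-point benefit. At N=136 and one-sided 2.5% the Z-test gives 73.0% there. The 21.4 points identifies the scenario simulated; it does not validate the printed power.
- That this error explains the whole gap between 85.0% and the 65.2% in Table 5-2. Of 19.8 points, about 5 come from the conversion on the table's footing; the other 14.6 (79.8 − 65.2) belong to the table-wide overstatement.
- That the trial is undersized for its target. The 86% at 25 points reproduces.

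This is a modest correction to a stated power, with no effect on the primary test or the conduct of the trial.

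**What to change.** Set the 20% row to odds ratio 2.333 in Protocol Table 5-3 (coefficient 0.847) and in SAP Table 5. Re-run it together with the other rows at the stated one-sided 2.5% and N=136, so that all rows share one footing. Re-running this row alone would leave it between a 53.8% and a 94.2% that do not reproduce at those settings. Report the power obtained, state the assumed risk effect, and reconcile the result with Table 5-2.

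If odds ratio 2.5 is kept, relabel the row in both documents as a 21.4-point difference, at center level and from a 50% control rate. That repairs the label but leaves the printed powers unreconciled with Table 5-2.

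The cost is one re-run of a small simulation and matching table edits in two documents. The downside is that the stated power for a 20-point effect becomes less favourable.
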